4. Women of childbearing potential (based on medical history) must consent to use a medically accepted method of birth control (e.g., condoms and spermicide, oral contraceptive, Depo-Provera injection, contraceptive patch, tubal ligation) or abstain from sexual intercourse during the time they are in the study and using transdermal nicotine.
5. If current or past diagnosis of bipolar disorder, eligible if:
 - a. No psychotic features
 - b. MADRS: total score less than 8 (past 4 weeks), suicidal item score less than 1 (past 4 weeks)
 - c. Y-MRS: total score less than 8 (past 4 weeks), irritability, speech content, disruptive or aggressive behavior items score less than 3 (past 4 weeks)
 - d. No psychiatric hospitalization or Emergency Room visits for psychiatric issues in the past 6 months
 - e. No aggressive or violent acts or behavior in the past 6 months
6. Able to communicate fluently in English.
7. Capable of giving written informed consent, which includes compliance with the requirements and restrictions listed in the combined consent/HIPAA form.

4. Key Exclusion Criteria

Subjects who self-report and/or present with the following criteria will not be eligible to participate in the study.

Smoking Behavior:

1. Current enrollment in a smoking cessation program, or use of other smoking cessation medications in the last month or plans to do either in the next 2 months.
2. Daily use of chewing tobacco, snuff and/or snus, or electronic cigarettes.

Alcohol/Drugs:

1. Self-report current alcohol consumption that exceeds 25 standard drinks/week over the past 6 months. Subjects will be told to limit or avoid the use of alcohol while in the study to avoid any adverse reactions to the study medication.
2. Current untreated and unstable diagnosis of substance dependence (eligible if past use and if receiving treatment and stable for at least 30 days). Current untreated and unstable diagnosis of substance abuse requires Study Physician approval.
3. A positive urine drug screen for cocaine, amphetamines, methamphetamines, PCP, barbiturates and ecstasy (MDMA) at Intake, or any testing session (see Measures and Table 1 for details). Participants believed to have a false-positive result may continue in the study, with investigator approval.

Medical:

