1. Females who self-report current pregnancy, planning a pregnancy during the study, or currently breastfeeding/lactating. All female subjects of child-bearing potential shall undergo a urine pregnancy test at the Intake, Baseline, PQ-Testing and 24-H Testing sessions.
2. Current diagnosis of unstable and untreated major depression, as determined by self-report & MINI (eligible if stable for at least 30 days).
3. Current or past diagnosis of psychotic disorder, as determined by self-report or MINI.
4. Suicide risk as indicated by at least one of the following on the MINI/CSSRS (the PI &/or PM (LCSW) will be consulted to assess safety and determine eligibility in cases close to the eligibility cutoffs):
 - a. Current suicidal ideation (within 30 days of enrollment)
 - b. Two or more lifetime suicide attempts or episodes of suicidal behavior
 - c. Any suicide attempt or suicidal behavior within 2 years of enrollment
5. Self-reported kidney and/or liver disease or transplant untreated/unstable or within the past 6 months.
6. Heart/Cardiovascular disease (e.g., angina, coronary heart disease, stroke, etc.) in the past 6 months.
7. Type-1 or type-2 diabetes.
8. Uncontrolled hypertension (BP systolic greater than 159 and/or diastolic greater than 99)*.
9. Liver function tests more than 20% outside of the normal range; Gamma-glutamyl Transpepsidase (GGT) values more than 20% outside of the normal range. If Albumin/Globulin ratios are 20% outside of normal range the abnormal value will be evaluated for clinical significance by the Study Physician and eligibility will be determined on a case-by-case basis.
10. Renal disease or renal dysfunction (e.g., serum creatinine levels ≥ 1.5 mg/dL [males], ≥ 1.4 mg/dL [females]).
11. A blood glucose level less than 70 mg/dl at any visit.

* Participants presenting with SBP greater than 159 mmHg and/or DBP greater than 99 mmHg at the Intake visit will be instructed to sit quietly for 10 minutes. Then the participant will have a second blood pressure reading taken after a 10-minute period. If, after the second reading the SBP greater than 159 mmHg and the DBP greater than 99 mmHg, the individual will be ineligible to participate, unless determined otherwise by the Study PI/Co-I or Study Physician, upon review.

Medication:

1. Current use or recent discontinuation (within the past 14 days) of any of the following medications:
 - a. Anti-anxiety or panic disorder medications (e.g., clonazepam, alprazolam).

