8. Not able to effectively communicate in English (reading, writing, speaking).
9. Missing 3 or more doses during the medication period determined by self-report.

5. Vulnerable Populations

No children under the age of 18, pregnant women, fetuses, neonates, or prisoners are included in this research study.

6. Populations vulnerable to undue influence or coercion

Educationally or economically disadvantaged persons or cognitively impaired persons will not be targeted for recruitment; however, they may be included in the current study. Because recruitment efforts for this study will be targeted to the greater Philadelphia area, University of Pennsylvania employees and students, and UPHS faculty and staff may be exposed to these advertisements and choose to respond. These individuals are eligible to participate if they meet all inclusion criteria. Status of participation in the current study will be independent of the participant's work or school activities.

7. Subject Recruitment

Participants will be recruited from several sources. Participants who have previously completed studies at our center and have agreed to be re-contacted for future studies will be contacted and invited to participate in this study. Additional recruitment via advertising (i.e., Craigslist, flyers, newspaper or TV ads) will be used to invite smokers from the general population.

Participants will be recruited from the Infectious Disease practices at the Hospital of the UPENN, Presbyterian Hospital, and Pennsylvania Hospital. The PMHARC will oversee the integration of this study into the clinics, ensuring access to

participants, collection of medical data (through UPHS PennChart medical record reviews and laboratory result requests), and access to private consulting rooms for screening at the clinics. These practices see over 500 patients monthly and more than 200 new patients each year.

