 1. Complete the consenting process remotely (per procedure outlined in the Informed Consent section) or in-person. Staff will review the consent form and answer all questions. Staff will then administer a comprehension questionnaire and review incorrect answers as needed. If completed remotely, subjects who are unable to provide an electronic signature may be mailed a physical version of the consent that must be signed and returned to us prior to continuing with the Intake tasks.
 2. Complete mental status exams (MINI and C-SSRS and MADRS, YMRS, Bipolar Disorder Additional Screener, if necessary) with trained research staff member.

3. Complete routine medical history (self-report), including concomitant medication review with a member of the research staff.
4. Complete the Shipley Institute of Living Scale
5. Complete baseline measures
6. Provide urine specimens for drug and (if applicable) pregnancy tests. Participants who test positive for either the urine drug screen and/or pregnancy test may be ineligible. Participants believed to have a false-positive result may continue in the study, with investigator approval.
7. Provide a CO breath sample.
8. Complete physiological measures such as blood pressure, height and weight.
9. Complete brief physical examination (led by a medical professional). If the provider is off-site this will be conducted via telehealth.
10. Provide an 8.5ml blood sample drawn for the assessment of liver function (LFTs and GGT enzyme levels) and creatinine levels. They will receive final confirmation of eligibility via phone call based on the blood test results.

If a participant meets the above eligibility criteria at the Intake, they will finalize their study schedule with staff.

Participants will be asked to refrain from using any study prohibited drugs (note: participants are allowed to take prescription medications not in the exclusion list) throughout their participation in the study.

- **Final Eligibility Phone Call.** When liver function tests have been reviewed and authorized by the Study Physician, a study staff member will call the subjects to inform them of their final eligibility.

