Urine Drug Screen. The urine drug screen will be administered at Intake and each testing session (baseline, day 21, and day 23). The urine drug screen requires about 30ml of urine and indicates whether the subject has recently taken any exclusionary drugs (cocaine, PCP, amphetamines, methamphetamines, ecstasy and barbiturates). Participants with a positive urine drug screen for any substance listed above other than THC, opiates, or methadone will be deemed ineligible. The rationale for excluding these participants is because one of the primary outcomes in this study is cognitive function. Thus, excluding individuals who screen positive for substances that may interfere with their ability to perform the cognitive tasks (e.g., benzodiazepines may slow reaction times) reduces this potential source of variability. In an effort to remain CLIA-compliant, results from urine drug screening will not be shared with participants. Participants will be informed that the testing is for research purposes only and that they will be informed of their eligibility status, but not of the specific testing results. In addition, the current protocol does not utilize PennChart and therefore, results of the screening will not be added to participants' electronic medical records.

Urine Pregnancy Test. At the Intake and each testing session (Baseline, day 21, and day 23), participants will be supplied with a simple, CLIA-waived urine pregnancy screen and informed that pregnant women are not advised to participate in this research study. Participants will then be instructed to administer the pregnancy test independently and will inform study staff if they would like to continue participation after they have administered the pregnancy screen. Participants will be informed that there is no penalty for discontinuing participation at this point in the visit and that they will still receive travel reimbursement for the visit.

Depression and Anxiety. The Hospital Depression and Anxiety Scale (HADS) [59], a 14-item self-report measure, will assess depression and anxiety symptoms. This scale correlates with clinical ratings of depression and anxiety [59] and is used with HIV-infected individuals [60]. Because depressive symptoms are associated with deficits in cognitive function [61] and lower HAART adherence [62], the HADS will be evaluated as a potential moderator of abstinence effects on cognitive function and relapse. The HADS will be administered at each visit.

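### The pregnancy-test procedure gives staff no step for learning the result, and after Intake no test-specific consequence of a positive is stated

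*Combined protocol and SAP*

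**What the plan says.** The only detailed procedure is the Urine Pregnancy Test paragraph of section 3.1. At four sessions the participant is given a urine test and is "informed that pregnant women are not advised to participate in this research study". She carries out the test herself and then "will inform study staff if they would like to continue participation after they have administered the pregnancy screen". Stopping at that point carries no penalty, and travel is still reimbursed.

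Other sections bear on the same test:

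- Key Exclusion Criteria, Medical, item 1, excludes "Females who self-report current pregnancy, planning a pregnancy during the study, or currently breastfeeding/lactating". It orders tests at the same four sessions but attaches no action to a positive. The sentence that opens the exclusion list is wider: it covers subjects who report a criterion or present with it.
- Vulnerable Populations: "No children under the age of 18, pregnant women, fetuses, neonates, or prisoners are included in this research study".
- Study Visits, Intake, item 6: "Participants who test positive for either the urine drug screen and/or pregnancy test may be ineligible". It adds: "Participants believed to have a false-positive result may continue in the study, with investigator approval".
- Baseline Session, item 2, and 24-H Testing Day Part 1, item 2, list the pregnancy test beside the drug screen and say what may follow a positive drug screen only. Day 21 repeats the Baseline activities.
- Privacy lists the pregnancy-test result among the information collected. Tissue Specimens requires a urine sample for both tests.
- Potential Study Risks, Pregnancy, concludes that metformin is not for use in pregnancy.
- Subject Compensation sets the payment for a subject who turns out to be ineligible at any visit.

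**The concern.** Read literally, the detailed procedure tells staff what the participant wants to do, not what the test showed. Two things follow.

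First, the Intake rule cannot operate. Neither the ineligibility decision nor the investigator-approved exception for a false positive can be applied unless staff know the result.

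Second, a woman who tests positive at Baseline and wishes to continue could start study drug, against the Vulnerable Populations statement and the risk section. A woman positive at Day 21 could go on taking it. Staff who instead work from the Intake, Privacy or Tissue Specimens text would learn the result and could act on it. The same positive test could therefore be handled in opposite ways depending on which section is followed, on a safety exclusion.

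**Working it through.** The protocol gives no figure to reproduce here. The check is a comparison of sections, followed by a count of the doses still ahead at each test.

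**Consequence of a positive result, by session**

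| Session | Drug screen | Pregnancy test |
|---|---|---|
| Intake | may be ineligible | may be ineligible; false-positive exception with investigator approval |
| Baseline (Day 0) | may be withdrawn | none stated |
| Day 21 | as Baseline, by reference | none stated |
| Day 23 | may be withdrawn | none stated |

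The Urine Drug Screen paragraph adds a general rule: "Participants with a positive urine drug screen for any substance listed above other than THC, opiates, or methadone will be deemed ineligible". The pregnancy paragraph that follows it has no counterpart. An explicit, test-specific consequence of a positive pregnancy test is thus given at 1 of 4 sessions, and at 0 of the 3 after Intake.

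**How each section stands to the Urine Pregnancy Test paragraph**

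- Intake, item 6: direct clash, because eligibility depends on a result the procedure does not deliver to staff.
- Privacy: a gap. The result is to be collected, but the procedure does not say how.
- Vulnerable Populations and the risk section: a difference in strength. Both are firm, whereas the test paragraph advises and leaves the choice to the participant.
- Exclusion-list opening and Subject Compensation: these imply that a pregnant participant is ineligible, and that ineligibility can arise at a later visit. Neither says that drug is withheld or stopped after a positive test.

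**Doses still ahead**

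Inputs, from Study Design and Drugs or Devices: one dose each evening on Days 1 to 23; low dose 500 mg throughout; high dose 500 mg on Days 1 to 7, 1,000 mg on Days 8 to 14 and 1,500 mg on Days 15 to 23.

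- Full course, low dose: 23 × 500 = 11,500 mg.
- Full course, high dose: 7 × 500 + 7 × 1,000 + 9 × 1,500 = 3,500 + 7,000 + 13,500 = 24,000 mg.
- After the Day 21 visit: 3 doses if that evening's dose is still to come, otherwise 2.
- After the Day 23 visit: 1 or 0 doses, by the same reasoning.

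| Positive at | Doses ahead | Low dose | High dose |
|---|---|---|---|
| Baseline | 23 of 23 | 11,500 mg | 24,000 mg |
| Day 21 | 2–3 (2/23 = 8.7%; 3/23 = 13.0%) | 1,000–1,500 mg (8.7–13.0% of course) | 3,000–4,500 mg (12.5–18.8% of course) |
| Day 23 | 0–1 (at most 1/23 = 4.3%) | 0–500 mg | 0–1,500 mg (at most 1,500/24,000 = 6.3%) |

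These are worst-case amounts in the two active arms. They measure how much a rule could prevent at each visit, not the risk of harm.

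**The case against.** The best defence is that the protocol as a whole already makes a pregnant woman ineligible. The exclusion list opens with wording that reaches anyone who presents with a criterion, pregnancy is its first medical item, and that item orders all four tests. Subject Compensation contemplates ineligibility at any session. This stands as far as it goes, and it rules out the reading that a positive test after Intake has no consequence at all. But the exclusion item itself is framed as self-report, and the compensation text is a payment rule. Neither tells staff what to do about study drug.

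A reader might also infer that staff are barred from knowing the result, or that the participant may report nothing beyond her wish to continue. The text does not say so. It does not forbid disclosure, and Privacy and Tissue Specimens suggest that the result is obtained. What is missing is a stated route.

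Self-testing with free withdrawal may be a deliberate choice to protect privacy. That is a fair reason, but it would still need reconciling with the Intake rule. Recording the result would add little that is new, since Privacy already lists it as collected.

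Finally, the situation should be rare. "Women of childbearing potential (based on medical history) must consent to use a medically accepted method of birth control" or abstain, planned pregnancy is excluded, and a test at Intake precedes Baseline by 2 to 30 days. The woman would also have to continue against advice and after the consent discussion of risks, and one of the three arms is placebo. All of this stands and limits the weight of the point.

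**Conclusion.** The point holds as an inconsistency in a safety procedure. The detailed test procedure has no step by which staff learn or record the result. It clashes with the Intake rule and is weaker than the two firm statements on pregnancy. After Intake no explicit, test-specific consequence of a positive is given, although the drug screen has one at Baseline and Day 23.

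The weight falls almost entirely on Baseline, where the whole course is still ahead. Day 21 concerns 2 to 3 doses, and at Day 23 there is almost nothing left to prevent.

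The documents do not support the inference that the trial intends to treat pregnant women, or that any would in practice be dosed. The protocol gives no pregnancy rate and no number of women of childbearing potential, so no expected count can be formed. The risk section reports no teratogenicity in rats and rabbits and no adequate studies in pregnant women, so the milligram totals cannot be read as harm. The Manual of Operations and the consent form are not among the documents and may say more; this conclusion concerns the protocol text alone. The dose counts assume the nominal visit and dosing schedule. No estimate, sample size or analysis is affected. The wording should be corrected because the correction is cheap and the present text allows opposite handling of the same result.

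**What to change.** Amend the Urine Pregnancy Test paragraph so that the participant shows or reports the result to staff and it is recorded at every scheduled test. Then state what a positive means:

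- Intake and Baseline: not eligible; no study drug dispensed or, if it has been mailed (as Baseline, item 9, allows), not started.
- Day 21: stop study drug and notify the Study Physician.
- Day 23: notify the Study Physician and follow up.
- One exception throughout, in line with the Intake text: a repeat test shows the first to have been a false positive and the investigator approves.

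Extend Medical exclusion item 1 to cover self-report or a positive pregnancy test. Replace the advisory sentence with wording as firm as Vulnerable Populations. Bring Intake item 6, Baseline item 2, Day 23 Part 1 item 2 and Tissue Specimens into line. Keep the assurances of no penalty and of travel reimbursement.

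The cost is protocol wording, one case report form field if none exists, and a repeat test for any positive; the tests themselves are already scheduled. The downside is slightly less privacy for the participant.

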3.2 Treatment Variables

Concomitant Medication Review. Subjects will be asked about their use of medications (over the counter and prescription) and substances that may alter subjects' response to the study medication. The Study Physician/Health Care Provider will advise as to whether other medications being taken are contraindicated and prescribe appropriate action from there (i.e., discontinuation of the study medication). The concomitant medication review will be completed at every study visit following the Intake.

Side Effects. A checklist of side effects based on the product insert will be administered at all study visits after the Intake. Checklists will be reviewed by staff following completion to confirm participant description of any experienced side effect matches the severity chosen, based on the severity classifications outlined on the form. The frequency and severity of common side effects of metformin will be rated on a 0 (none) to 3 (severe) scale. An open-ended side effects question will also be included. Furthermore, participants will receive written instructions to call the Health Care Provider/Study Physician should they experience any severe side effects or adverse events between study visits.

Pill Count/Adherence. Medication adherence will be assessed by pill count at each study visit [65].

3.3 Primary Outcomes

Mood: Positive and Negative Affect. The Positive and Negative Affect Schedule (PANAS) [66], a 20-item Likert-format self-report measure, will be used to assess Positive Affect (PA; 10 items, e.g., enthusiastic, strong) and Negative Affect (NA; 10 items, e.g., distressed, upset), two dominant and generally orthogonal dimensions of affect. PA and NA (PANAS) will be assessed at all study visits (except the Intake). PA and NA will be assessed using a "past week" time reference for all visits except the 24-h testing visit on Day 23, which will use a 24-h time reference.

Neurocognitive Measures. Neuropsychological tests will be administered in a quiet laboratory testing room on a Dell® desktop computer running on the most recent and compatible version of Windows® at the CIRNA. Unless otherwise noted, all tasks will be administered via E-Prime 2.0 (Psychology Software Tools, Inc.). The computerized battery is administered in a random order using clickable icons. Total administration time is ~ 45 min. The tasks are:

- N-back Working Memory Task: In the traditional N-back task, sequences of letters or numbers are displayed and subjects respond with a button press to a single target using the following rules. The version of the N-back used in this study utilizes fractal images in place of letters or numbers. During the 1-back condition, subjects respond if the image is identical to the one preceding it. In the 2-back condition, they respond if the stimulus is identical to the one two trials before. In the 3-back condition they respond if the image is identical to the one three trials before. The active baseline condition (0-back) is a simple target detection task. The primary outcomes will be total correct and correct reaction time (task duration: ~18 minutes).
- Stop Signal Task (SST): The SST is a measure of response inhibition, or the ability to inhibit a prepotent response, and has been used in previous work with smokers [13]. In this task, participants are instructed to press labeled keyboard keys as quickly and as accurately as possible to indicate the direction the arrow faced ("z" for left; "/" for right). Following a 32-trial practice, stop signals (an 800-Hz, 100-ms, 70-dB tone) are presented on 25% of trials for a 32-trial practice and three task blocks of 64 trials each. The initial stop delay in each block is 250 ms and adjusts by 50 ms increments depending on whether the participant is able to successfully inhibit a response [67]. The adjusting stop delay allows the determination of the delay at which inhibition occurs on approximately 50% of trials. All trials consist of a 500-ms warning stimulus followed by a 1,000-ms go signal (left- and right-facing arrows) and 1,000-ms blank screen intertrial interval. Mean RT for each block is calculated based on valid responses (i.e., RT greater than 200 ms),

and only blocks with 20–80% inhibition and at least 80% accuracy are included in analyses. Stop signal reaction time (SSRT) is the primary dependent variable and is calculated by subtracting the mean stop delay from the mean RT on go-trials (task duration: ~10 minutes).

- **Color Shape Task:** The Color Shape Task is a measure of flexibility. In each trial of this task ([Miyake, Emerson, Padilla, & Ahn, 2004](#)), a cue letter (C or S) appears above a colored rectangle with a shape in it (outline of a circle or triangle). Participants are instructed to indicate whether the color is red or green when the cue is C, and whether the shape was a circle or triangle when the cue is S. The colored rectangles are approximately 1.7” wide and 1.4” high, the circles were approximately 1.1” in diameter, and the triangles were 1.25” on each side. The color-shape figure appears in the center of the screen and the cue letters are centered 3/8” above its top edge.
- **HVLT Task:** The Hopkins Verbal Learning Test – Revised (HVLT-R) assesses verbal learning and memory (immediate recall, delayed recall, delayed recognition) (Brandt, 1991). The task has been validated in individuals 16 to 92 years old and within brain-disordered populations (e.g., Alzheimer’s disease, amnesic disorders) as a measure of verbal learning and memory (Benedict et al., 1998). There are six alternate forms, each consisting of a list of 12 nouns (targets) with four words drawn from each of three semantic categories. The semantic categories differ across the six forms, but the forms are very similar in their psychometric properties. The HVLT-R has high test-retest reliability, and its construct, concurrent, and discriminant validity have been well-established (Shapiro et al., 1999). Raw scores are derived for Total Recall, Delayed Recall, Retention (% retained), and a Recognition Discrimination Index. Verbal memory has been shown to be a cognitive domain negatively affected by HIV infection (Antinori et al., 2007; Robertson and Yosief, 2014; Woods et al., 2004). There are two primary outcomes: Total Recall and Delayed Recall. Task duration is 5-10 min with a 25-min delay.
- **Delay Discounting Task:** In this paradigm, participants choose between a smaller reward available immediately (e.g., \$500 today) and a larger reward available after a longer delay (e.g., \$1000 in a month). In this task, people differ in their degree of *delay discounting*, the extent to which they forgo larger monetary magnitudes in the future in order to obtain immediate rewards. As in previous work, the delayed reward will be fixed (e.g., \$1000) and the magnitude of the immediate reward adjusts based on the subject’s responses (Du et al., 2002). Subjects will make 42 choices (6 trials for each of 7 delays: 1 day, 1 week, 1 month, 3 months, 1 year, 5 years, and 25 years). The primary behavioral outcome will be the subject’s *discount rate*. Discount rates will be estimated by fitting a logistic regression that assumes a person’s decisions are a stochastic function of the difference in subjective value between the two options (Wileyto et al., 2004). Keeping with standard behavioral findings (Kable and Glimcher, 2007, 2010; Kirby and Santiesteban, 2003; Mazur, 1987), we will assume that subjective value (SV) is a hyperbolic function of the reward amount (A) and delay (D): $SV = A/(1+kD)$, where *k* is the participant’s discount rate. Larger values of *k* indicate a greater degree of discounting future rewards. Participants will be told that the questions are hypothetical and that they should make their choices according to what they would choose if they were going to receive that amount. Task duration: approximately 5 minutes.

